9.2 Randomization, blinding and treatment allocation

Four hundred and fifty elderly subjects with RA, will be randomized to either prednisolone 5 mg/day or matching placebo, both added to existing anti-rheumatic treatment in a 1:1 ratio. The two groups are double-blinded.

Randomisation will be stratified for participating study site, for prior exposure to GC, and for concurrent start of other anti-rheumatic therapy.

For randomisation, an Interactive Web Response System (IWRS) will be integrated in the data management system. The minimization randomisation method based on the principles of Pocock and Simon ([Pocock SJ 1975](#)) will be used. Minimization is a method of randomization that allocates subjects to the treatment group that best maintains balance in stratifying factors. It is effective even at small sample sizes and with multiple stratification variables. Rules to calculate the amount of variation and the imbalance for each treatment, and rules to assign a probability to each treatment will be discussed with the sponsor before the implementation.

For the substudy to measure the effect of smart reminders to adherence, 50 subjects with a smartphone will be randomized, between an application loaded on their smartphone that communicates with an adherence monitoring device loaded into the cap of the drug bottle and no such application loaded on their smartphone. Randomisation will be stratified for participating country and treatment in order to have for each treatment a balance between an application and no application on the smartphone. The same method as mentioned before will be used.

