#### 4.10.1.1 Full model

We model the treatment outcome by a mixed effect model with fixed effects measurement occasion after baseline (d), baseline measurement (Z), treatment condition (T), and random effects across individuals (level 2; random intercept U) and study centers (level 3; random intercept V).

Furthermore, we include the strata of the GLORIA trial (S) as fixed effects. Centers could also be modeled as fixed effects, but we have chosen random effects because several centers have included only a very low number of patients. A compound symmetry correlation structure is assumed.

We write down mixed effect model 1 as:

$$\begin{aligned}
 Y_{ijk} &= \beta_{0jk} + \sum_{s=1}^4 \beta_{1jks} d_{ijks} + \epsilon_{ijk} && \text{(level-1 model)} \\
 \beta_{0jk} &= \delta_{00k} + \delta_{01k} S_{jk1} + \delta_{02k} S_{jk2} + \delta_{03k} T_{jk} + \delta_{04k} Z_{jk} + U_{0jk} && \text{(level-2 model for intercept)} \\
 \beta_{1jks} &= \delta_{10ks} && \text{(level-2 model for slope)} \\
 \delta_{00k} &= \gamma_{000} + V_{00k} && \text{(level-3 model for intercept)} \\
 \delta_{01k} &= \gamma_{010} && \text{(level-3 model for slope)} \\
 \delta_{02k} &= \gamma_{020} && \text{(level-3 model for slope)} \\
 \delta_{03k} &= \gamma_{030} && \text{(level-3 model for slope)} \\
 \delta_{04k} &= \gamma_{040} && \text{(level-3 model for slope)} \\
 \delta_{10ks} &= \gamma_{100s} && \text{(level-3 model for slope)}
 \end{aligned}$$

with  $U_{0jk}$  the individual-level random effect,  $V_{00k}$  the center-level random effect, and  $\epsilon_{ijk}$  the residual.

The indices:

- i= 1,..., m : fixed measurement occasion after baseline (in GLORIA, m=5)
- j= 1,...,n : individuals
- k=1,...,K : study centers (currently, K=28 in GLORIA)

The variables:

- $Y_{ijk}$  : DAS28 outcome
- $d_{ijks}$  : dummy variables encoding the five measurement occasions after baseline, s=1,..., 4
- $T_{jk}$  : treatment indicator, 0 if placebo, 1 if active (prednisolone) treatment
- $Z_{jk}$ : Baseline measurement of DAS28
- $S_{jk1}, S_{jk2}$ : Stratification factors

The parameters:

- $\gamma_{000}$ : the model intercept
- $\gamma_{010}$ : fixed effect of stratification factor 1
- $\gamma_{020}$ : fixed effect of stratification factor 2
- $\gamma_{030}$ : fixed effect of treatment
- $\gamma_{040}$ : fixed effect of baseline measurement of DAS28
- $\gamma_{100s}$ : effect of time dummy s

And the random effects :

- $U_{0jk}$  : random intercept of individual i

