#### 4.10.3 Model and statistical test for the effect of treatment on harm: SAEs or other AESIs (Hypotheses 3)

Contrary to the hypothesis set 1 on the benefit of prednisolone treatment, hypotheses 3 require testing the difference in probabilities of encountering at least one SAE or other AESI over 24 months. On marginal level it would be sufficient to estimate these probabilities after  $t=24$  months and evaluate the significance of their difference. However, to additionally account for the stratification of the GLORIA design, we apply a logistic mixed-effects regression (model 3):

$$P_{jk} = g^{-1}(\delta_{0k} + \delta_{1k}S_{jk1} + \delta_{2k}S_{jk2} + \delta_{3k}T_{jk} + U_{jk})$$

$\delta_{0k} = \gamma_{00} + V_{0k}$	(level-2 model for intercept)
$\delta_{1k} = \gamma_{10}$	(level-2 model for slope)
$\delta_{2k} = \gamma_{20}$	(level-2 model for slope)
$\delta_{3k} = \gamma_{30}$	(level-2 model for slope)
$\delta_{4k} = \gamma_{40}$	(level-2 model for slope)

where now  $P_{jk}$  the probability of patient  $j$  in center  $k$  to encounter at least one SAE or other AESI over 24 months. The function  $g^{-1}$  denotes the inverse of the log link. Significance of  $\delta_{3k}$  will be evaluated with a t-test. Note that model 3 uses the log link as opposed to, for example, the logit link to estimate and test relative risk.

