Given the above we can now assume with confidence that the base rate of patients with events in the placebo group will be substantially higher than originally predicted. This adds power to the trial: we need only between 400 and 450 patients to detect the originally targeted contrast of 27.5%/20% = relative risk of 1.38 (Table 1). At the expected pooled event rate of 40%, with 400 patients we have 80% power to detect a difference of 12% between placebo and prednisolone: i.e. placebo 34% and prednisolone 46%, a relative risk of 1.35. The results are better with 450 patients, and when the event rate is higher (Table 1). At the moment of submission of the amendment trial recruitment has been closed on December 31, 2018 at a total of 452 patients.

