**Table 1. Sample size scenarios (one-sided alpha 5%).**

expected event rate over 2 years		with power 80%,			
(% unique patients with at least one event)		detectable rate in predn group		Relative Risk	
pooled	placebo	n=400	n=450	n=400	n=450
30%	26%	38%	37%	1,47	1,43
35%	30%	42%	41%	1,40	1,37
40%	34%	46%	45%	1,35	1,32
45%	39%	52%	52%	1,31	1,31
50%	43%	55%	55%	1,28	1,28

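### The primary harm model (SAP model 3) is mis-specified as written, is likely to fail to fit, and has no named fallback; the effect scale is also stated inconsistently.

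*SAP*

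**What the plan says.** SAP 4.10.3 calls model 3 a logistic mixed-effects regression, but the same section ends: "Note that model 3 uses the log link as opposed to, for example, the logit link to estimate and test relative risk". The outcome is the probability that a patient is "to encounter at least one SAE or other AESI over 24 months", so each patient contributes one binary value.

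The linear predictor contains an intercept, two stratification factors, treatment and a term U_jk indexed by patient and centre. The intercept has a random centre effect V_0k. U_jk is not defined in the section. A line setting delta_4k equal to gamma_40 follows, although no delta_4k term stands in the predictor.

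Other parts of the plan bear on this:

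- In model 1 (SAP 4.10.1.1) the corresponding U term is the random effect of a patient with repeated DAS28 values. In model 2 (SAP 4.10.2) U_jk is the residual of a linear model, and delta_4k multiplies baseline damage.
- SAP 4.10.2 names a bootstrap alternative if damage scores are strongly skewed. SAP 4.10.3 names no alternative.
- There are 28 centres, and SAP 4.10.1.1 says that "several centers have included only a very low number of patients".
- SAP 4.9.1 states the harm hypothesis as a ratio of probabilities, whereas SAP 4.10 says that harm will be estimated by an odds ratio. Protocol 11.1 names a chi-square test as the main analysis and logistic regression as secondary.
- SAP 4.12 reads non-significant increases against upper limits of 1.2 and 1.3 without saying whether these are relative risks or odds ratios.

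**The concern.** A patient random effect needs more than one observation per patient, or a distribution with a free residual variance. A binary outcome recorded once offers neither. The delta_4k line has no data attached.

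The more practical problem is the log link. It requires every fitted log-probability to be at or below zero, while a normal centre effect has no upper bound. With events near 40% the room is small, and very small centres make the centre effect hard to estimate.

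If the fit fails, the plan gives no rule for what comes next. The analyst would then choose among a logit model, a model without centres and an unadjusted test, possibly after unblinding. That choice would be made on a primary outcome tested at one-sided 5%, which decides whether harm is labelled success or failure.

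**Working it through.** **Inputs.** From SAP 6: "with 400 patients we have 80% power to detect a difference of 12% between placebo and prednisolone", that is "placebo 34% and prednisolone 46%, a relative risk of 1.35", at one-sided 5%; recruitment "closed on December 31, 2018 at a total of 452 patients". From Protocol 9.2: the two treatments, "both added to existing anti-rheumatic treatment in a 1:1 ratio". This gives 200 per arm for the planning case and 226 per arm for the trial as recruited.

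**1. The plan's own figure.** With pooled rate 0.40, z = [0.12 × √200 − 1.645 × √(2 × 0.40 × 0.60)] / √(0.34 × 0.66 + 0.46 × 0.54) = (1.697 − 1.140) / 0.688 = 0.81. Power is 79.1%, against the stated 80%. The figure reproduces, and nothing below changes it.

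**2. U_jk.** With a log link and U ~ N(0, s²), the marginal probability is exp(η + s²/2), where η is the rest of the predictor. The variance is therefore absorbed by the intercept. For 77/226 against 104/226 events, without centre or strata:

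| s | maximised log-likelihood | intercept | treatment coefficient |
|---|---|---|---|
| 0 | −300.9136 | −1.077 | 0.3006 |
| 0.2 | −300.9136 | −1.097 | 0.3006 |
| 0.4 | −300.9136 | −1.157 | 0.3006 |
| 0.6 | −300.9136 | −1.257 | 0.3006 |

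The variance of U is not identified. The treatment log-RR, ln(104/77) = 0.3006, is.

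**3. delta_4k.** Taken as a parameter without a covariate, it leaves the design at rank 4 of 5. Without it the design has full rank. Since it does not enter the predictor, it is a clerical leftover, most likely from model 2 (an inference from the matching notation).

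**4. Room under the log link.** ln(0.46) = −0.777. With a normal effect of SD 0.4 and the mean held at 46%, the probability passes 1 at (0.777 + 0.4²/2) / 0.4 = 2.14 SD, an upper tail of 1.6%. At SD 0.6 the share is 5.5%.

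**5. Does it fit?** The documents give neither centre sizes nor centre variation, so these were assumed: 452 patients, 28 unequal centres, and centre SD on the log scale of 0.1 to 0.4 (0.1 to 0.5 in the second and third checks).

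- R (named in SAP 8), glmer in lme4, binomial with log link: with U_jk it stopped with an error in every data set tried. Without U_jk it stopped in about 75% to 100%, with or without starting values.
- A separate quadrature fit of the random-centre model gave optimiser warnings in 18% to 49% of data sets, and its fitted random-effect range reached probabilities above 1 in 39% to 99%. This was purpose-written code and is only indicative.
- A log-binomial model without random effects converged in 600 of 600 data sets. The difficulty therefore lies in combining the log link with the centre effect.
- A log-link Poisson model with robust variance fitted every data set. In the runs of the second check, mean RRs were about 1.32 to 1.38 both for the Poisson fit clustered by centre and for the random-centre model.

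**6. What a change of scale does.** Unadjusted Wald and score tests, 226 per arm, one-sided p:

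| events, placebo vs prednisolone | RR | OR | p, log-RR | p, log-OR | p, score |
|---|---|---|---|---|---|
| 77 vs 91 | 1.18 | 1.30 | 0.0872 | 0.0867 | 0.0865 |
| 77 vs 94 | 1.22 | 1.38 | 0.0504 | 0.0498 | 0.0496 |
| 77 vs 104 | 1.35 | 1.65 | 0.0052 | 0.0049 | 0.0048 |

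The p-values nearly coincide, and only a knife-edge result crosses 5%.

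The SAP 4.12 category is different. For 90 vs 95 events the one-sided 95% upper limit is 1.27 as an RR (the inconclusive middle category) and 1.50 as an OR (a trend towards more events). This is general at this sample size. The variance of the log-OR is at least 8/226 = 0.0354, so its SE is at least 0.188. Even at OR = 1 the upper limit is at least exp(1.645 × 0.188) = 1.36. On the OR scale, every non-significant increase would fall in the least favourable category.

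**The case against.** A reader might infer that the primary harm model cannot be estimated at all and that the harm test is therefore void. The documents do not support that. The tested parameter is identified whatever the variance of U. The delta_4k line touches nothing in the predictor, and an experienced analyst would drop both symbols and fit treatment, two strata and a random centre intercept.

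A reader might also infer that the choice of replacement would decide the p-value. Among the log-RR, log-OR and score tests it would not, except at the very edge of 5%. Nor is a choice after unblinding certain: it arises only if the fit fails, and failure here is simulated under assumed centre sizes and variation, not observed.

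Simpler analyses are also on the page. Protocol 11.1 has the chi-square test, and SAP 4.10.3 accepts that a marginal comparison would suffice were it not for the stratification. Neither is designated as a fallback, however, so the gap in pre-specification stands, as does the conflict between odds ratio and relative risk.

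A Poisson model with centre-clustered variance is not free of problems either. In a null simulation of 2,000 data sets (452 patients, 28 unequal centres, assumed centre SD 0.25), it rejected 6.6% at a nominal 5%, against 5.1% for the unclustered robust variance, with Monte Carlo error of about 0.5 points.

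**Conclusion.** The point holds as a mis-specification with a missing fallback on a primary outcome. It does not show that the treatment effect is inestimable. U_jk should not be in the model, and the delta_4k line is an orphan. The remaining log-link model with normal centre effects is likely to fail in standard R software, given event rates near 40% and 28 centres of very unequal size. That likelihood rests on assumed centre sizes and variation; the identifiability results do not.

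No sample-size or power figure changes, and the p-value is nearly unaffected by the link. The consequence lies in the effect scale. At the planning rates the same data read as RR 0.46/0.34 = 1.35 or OR (0.46/0.54)/(0.34/0.66) = 1.65. The choice decides which category of SAP 4.12 a non-significant increase receives. That ambiguity is in the plan whether or not the model converges. The change should be made before unblinding.

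**What to change.** 1. In SAP 4.10.3, delete U_jk from the predictor and delete the delta_4k line.
2. State that the effect measure is the relative risk. Correct the description of the model as logistic in SAP 4.10.3 and the reference to an odds ratio in SAP 4.10, and state in SAP 4.12 that the limits (1.2 and 1.3, and likewise 0.7 and 0.8) apply to the relative risk.
3. Make the primary model a log-link Poisson model with treatment and the two stratification factors and a robust variance. Alternatively, keep the log-binomial centre model and name the Poisson model as its replacement, with an explicit definition of failure to converge.
4. Specify the variance as unclustered robust, or as clustered on centre with a named small-sample correction.

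The cost is a few lines of SAP text and standard software. The statistical price is that the unclustered version no longer models centre explicitly, although centre was a balancing factor at randomisation.

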#### 4.11 Evaluation of possible confounded results due to differential co-intervention

The data collected according to the GLORIA protocol are intended to allow a comparison of the effect of prednisolone treatment over placebo in terms of benefit and harm. Given that GLORIA is a pragmatic trial where changes in concomitant treatment (co-interventions for RA, i.e. antirheumatic co-medication) are allowed, an estimation of “pure effects” (i.e. without changes in concomitant treatment) is not possible. When changes in antirheumatic treatment differ between the groups this can result in a confounded estimate of the “pure” effects. Most changes in co-medication can be expected to lower the chance of finding a difference in efficacy between the treatment groups, because negative consequences of being in the placebo group can be countered by changing antirheumatic therapy. For this reason, we also analyze the short-term efficacy of prednisolone in the first three months in a per-protocol population where the chance of confounding is minimized. Note: adverse events leading to stop of study medication are part of the primary harm outcome, and are not covered here.

We will test for potential confounding of the efficacy results. We will not test for confounding of the harm results, because straightforward interpretation is difficult: harm and changes in medication are probably related to each other in a complicated way.

#### 4.11.1 Testing and correcting for differential treatment changes

We plan to check for substantial confounding by comparing the incidence of lasting and substantial changes in co-medication categorized by the reason for change. For practical reasons, we will only consider the first instance of such a change in co-medication. Lasting means we do not consider brief starts or interruptions (i.e., lasting no more than 6 weeks); we also disregard changes in patients stopping the study medication within 3 months following the change.

We will only consider changes that occur in the period starting at 3 months (V2) and 15 months (V6), because the potential for confounding is greatest in this period. Changes before V2 are too early to create confounding, and changes beyond V6 have relatively little effect on the outcome (effect on measurement at V7 and V9). Co-medication includes all disease-modifying antirheumatic drugs (conventional, biologic and targeted), and GC treatment classified as protocol violation and adjudicated in case of oral use.

Oral GC treatment is adjudicated to select occurrences with potential for confounding similar to that of other antirheumatic drugs. Periods of oral treatment up to 3 weeks for RA are equated to one im injection for RA. More than two of either in the period assessed will count as intensification.

Oral GC treatment for comorbidity creates less potential for confounding. More than 4 periods of oral treatment for comorbidity lasting no more than 3 weeks will count as intensification.

Any period of oral therapy longer than 3 weeks for any indication (RA or otherwise) will also count as intensification.

We distinguish 3 reasons for co-medication changes:

1. Lack of efficacy: this includes instances of
  - a. co-medication intensification: increase dose of current antirheumatic drug(s), or adding a new drug (co-medication) to the current treatment, including adjudicated GC treatment classified as protocol violation;
  - b. co-medication switch (replacing one antirheumatic drug with another);
2. Adverse event: co-medication switch, or stop of an antirheumatic drug and start of another later; sole dose reduction for adverse event is not considered a substantial change;
3. Good efficacy: co-medication taper: decrease dose or stop of current medication(s) without addition of or replacement by another medication.

The remaining patients will be categorized as having no change in co-medication.

For every patient we record and categorize the reason (lack of efficacy, adverse event, good efficacy) for the first change in co-medication in the specified time period. If an adverse event was reported at the moment of change(s) in medication, we will assume that the medication is changed due to adverse events.

Otherwise, if a patient has no reported adverse event(s) at the moment of:

- intensifying or switching the medication: we will assume that the treatment is changed due to lack of efficacy;
- lowering or stopping co-medication: we will assume that the change is due to good efficacy.

Situations that are unclear will be adjudicated by the medical monitor before the blind is broken.

The effect of the co-medication change on the expected DAS28 depends on the reason: in case of lack of efficacy or adverse event, the change is expected to lead to a better outcome: a new drug or

an increased dose of the same drug is expected to work better. In case of good efficacy the change is expected to lead to the same or worse outcome: tapering a drug will most likely increase the DAS28 somewhat and may cause a flare.

Therefore, for both treatment groups we will calculate:

1. the sum of patients experiencing a co-medication change for lack of efficacy, and for adverse events; and
2. the number of patients experiencing a co-medication change for good efficacy.

We will express 1) and 2) as proportion of the total number of patients in each treatment group and compare these between the groups with two Z-tests (each one-sided at  $p<0.025$ ).

The null hypotheses are:

$H_{0,4a}$  : The probability of experiencing a co-medication change for lack of efficacy or for adverse events in the placebo group is lower than or equal to the probability in the prednisolone group.

$H_{1,4a}$  : The probability of experiencing a co-medication change for lack of efficacy or for adverse events in the placebo group is higher than the probability in the prednisolone group.

$H_{0,4b}$  : The probability of experiencing a co-medication change for good efficacy in the placebo group is higher than or equal to the probability in the prednisolone group.

$H_{1,4b}$  : The probability of experiencing a co-medication change for good efficacy in the placebo group is lower than the probability in the prednisolone group.

We will assume confounding to the detriment of active treatment if:

1.  $H_{0,4a}$  is rejected significantly at  $p < 0.025$  OR
2.  $H_{0,4a}$  is rejected significantly at  $p < 0.025$

Assessing potential for confounding by co-medication changes in the analyses regarding harm of prednisolone is more difficult. Harm and changes in medication are probably related to each other in a complicated way. Therefore, we will not examine this.

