## 4.10 Modeling and estimating

The testing of the hypothesis sets requires estimating the average effect of treatment on benefit (operationalized as DAS28 and progression of joint damage) and harm (operationalized as encountering at least one SAE or other AESI). An observed effect with a probability of occurrence under the (one-sided) null hypothesis (p-value) of 5% or less will be considered significant causing us to reject the null and to accept the alternative hypothesis. The hypotheses and their tests are one-sided in view of pre-existing knowledge for benefit and the likelihood that true benefit will be underestimated in the context of the pragmatic design and potential differential co-intervention (see section 4.11); and for harm because of limited power. This results in a higher chance of declaring benefit, but also a higher chance of declaring harm.

The average effect of treatment on DAS28 (hypotheses 1) and damage progression (hypothesis 2) will be estimated in a mixed effects regression model. The exact form and empirical fit of the model are important determinants of the power of the statistical test of the treatment effect parameter, as described below. Hypotheses 3 require estimation of the difference in probability to encounter a SAE or other AESI between treatment and placebo over 24 months, which will be implemented by estimating the odds ratio of a SAE or other AESI in treatment versus placebo. All analyses will also take into account that the GLORIA study uses a stratified sampling design, where within each of 28 participating centers randomization is executed stratified by earlier exposure to glucocorticoids (yes/no) and start or switch of other anti-rheumatic drugs at the beginning of the trial.

We first describe how hypothesis testing for the GLORIA study will be executed. In this exposition, we assume that the observed data matrix is complete and that the estimated effects are not confounded with treatment changes. We describe methods to address incomplete data (section 4.2) and to assess confounding with treatment changes (section 4.11).

Our general analysis strategy can be summarized as follows:

1. Test hypotheses 1 to 3 with models described in this section and missing-at-random data correction (section 4.2).
2. Execute robustness checks for monotonous not-missing-at-random data pattern with non-responder imputation (NRI; section 4.2).
3. Assess confounding with treatment changes (section 4.11)

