## 4.12 Interpretation rules

The outcomes of benefit (disease activity and damage progression) and harm (number of patients with at least one SAE or other AESI) will be interpreted simultaneously.

The outcomes of benefit will be interpreted as follows (prednisolone group compared to placebo; reference to the specific rejected null hypotheses in parentheses):

1. success:
  - a. lower disease activity ( $H_{0,1a}$ )  
AND lower damage score ( $H_{0,2a}$ )
  - b. lower disease activity OR lower damage score; AND confounding ( $H_{0,4a}$  or  $H_{0,4b}$ )
2. partial success/tradeoff:
  - a. lower disease activity OR lower damage score AND NO confounding
  - b. NO lower disease AND NO lower damage progression AND confounding
3. failure: NO lower disease activity AND NO lower damage score AND NO confounding.

The outcomes of harm will be interpreted as follows:

1. success: NO significant increase in AEs
2. failure: significant increase in AEs ( $H_{0,3a}$ )

Combined assessment of benefit and harm

- a. Success: success in benefit and harm
- b. Failure: failure in benefit and harm
- c. Partial success/tradeoff: all other scenarios

For further interpretation of increases in the occurrence of SAE or other AESI in the active treatment group that did not reach significance, we will use the suggestions of the GRADE (Grades of Recommendations, Assessment, Development, and Evaluation) Working Group (Guyatt 2012), upper limit of one-sided 95% confidence interval (CI):

1.  $> 1.3$ : GC associated with a trend towards greater occurrence;
2.  $\leq 1.2$ : GC appears to have little effect on the occurrence;
3.  $> 1.2$  and  $\leq 1.3$ : results failed to demonstrate or exclude a greater occurrence.

In the case of a numerical DECREASE in the occurrence of SAE or other AESI in the active treatment group, a more stringent test for significance will be performed ( $p < 0.025$ ).

For the interpretation of decreases that did not reach significance:

lower limit of one-sided 95% CI:

1.  $< 0.7$ : GC associated with a trend towards reduced occurrence;
2.  $\geq 0.8$ : appears to have little effect on the occurrence;
3.  $< 0.8$  and  $\geq 0.7$ : results failed to demonstrate or exclude a reduced occurrence.

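### The two co-medication Z-tests omit the minimisation factors; if those factors predict co-medication changes, the tests are conservative and lose some power

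*SAP*

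**What the plan says.** Protocol 9.2 states: "Randomisation will be stratified for participating study site, for prior exposure to GC, and for concurrent start of other anti-rheumatic therapy". The method is described as "The minimization randomisation method based on the principles of Pocock and Simon". Its assignment probability is not given; the "rules to assign a probability to each treatment will be discussed with the sponsor before the implementation".

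SAP 4.10 makes a general commitment: "All analyses will also take into account that the GLORIA study uses a stratified sampling design". The same section then lists the assessment of confounding by treatment changes as step 3 of the general analysis strategy. Models 1 (DAS28), 2 (damage) and 3 (harm) each carry the two patient-level strata and a centre effect. For harm, SAP 4.10.3 remarks that a marginal comparison would be enough but adopts a mixed model in order to respect the stratification.

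SAP 4.11.1 handles H0,4a (change for lack of efficacy or adverse event) and H0,4b (taper for good efficacy) differently. It counts each patient's first qualifying change between V2 and V6, expresses the counts "as proportion of the total number of patients in each treatment group", and will "compare these between the groups with two Z-tests (each one-sided at" 2.5%). No centre or stratum term is named, and no reason is given for leaving them out.

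SAP 4.12 then uses the result. One positive benefit outcome counts as full success under the condition "lower disease activity OR lower damage score; AND confounding", and as partial success without confounding. With neither benefit outcome positive, confounding separates partial success from failure.

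**The concern.** Minimisation removes most of the chance difference between arms that comes from the factors it balances. A two-sample Z-test still includes that component in its standard error. When the factors are prognostic for the outcome tested, the test rejects less often than its nominal level under the null and has less power than an adjusted test.

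A link with co-medication changes is plausible for centre. Protocol section 3 describes RA treatment as differing widely across Europe, and SAP 1.1 lists 28 hospitals in seven countries. For prior glucocorticoid exposure and concurrent start the documents offer no evidence either way.

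What is at stake is sensitivity. A non-significant pair of tests is read as absence of confounding, which is a required element of the failure verdict. SAP 4.10 also justifies one-sided testing partly by the risk that differential co-intervention hides true benefit. These two tests are the check for that risk.

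**Working it through.** **Inputs from the documents.** Two tests, each one-sided at 0.025 (SAP 4.11.1); 452 patients (SAP 6), 1:1 allocation (Protocol 9.2), 28 centres (SAP 4.10).

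**Inputs not in the documents, assumed.** Assignment probability 0.8; prior glucocorticoid exposure 45%; concurrent start 15%; placebo change rate 20% or 35%, with an absolute difference of 10 or 12.5 points respectively; all factor effects.

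**Step 1: the stated level.** 1 − Φ(1.96) = 2.50%, correct if the test's independent-sample variance is correct. The SAP states no power for these tests.

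**Step 2: formula.** Let the balanced factors explain a share R² of outcome variance, and put s = √(1 − R²). With full balance the true standard error is s times the one the Z-test uses, so:

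- true level = 1 − Φ(1.96/s)
- Z-test power, where the adjusted test has 80%, = Φ(1.96 + 0.8416 − 1.96/s)

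For R² = 5%: s = 0.9747 and 1.96/s = 2.011, so the level is 2.22% and power is Φ(0.791) = 78.5%.

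| R² | True level | Z-test power (adjusted 80%) |
|---|---|---|
| 0% | 2.50% | 80.0% |
| 2% | 2.39% | 79.4% |
| 5% | 2.22% | 78.5% |
| 10% | 1.94% | 76.9% |
| 15% | 1.68% | 75.0% |
| 20% | 1.42% | 72.9% |
| 30% | 0.96% | 67.7% |

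**Step 3: simulation.** Pocock-Simon minimisation on the three factors with unequal centres. The pooled Z-test is compared with a linear probability model containing centre, prior glucocorticoid exposure and concurrent start. There were 20,000 null and 8,000 power replicates per scenario. Monte Carlo SE is √(0.025 × 0.975/20,000) = 0.11 points for the level and about √(0.85 × 0.15/8,000) = 0.40 points for each power. Paired entries are for placebo rates of 20% / 35%.

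| Association (centre SD, log-odds; odds ratio of each other factor) | R² | Z-test level | Adjusted level | Power, Z v adjusted, 20% | Power, Z v adjusted, 35% |
|---|---|---|---|---|---|
| None (0; 1) | 0% | 2.44% / 2.60% | 2.43% / 2.59% | 85.6% v 84.4% | 84.0% v 83.4% |
| Weak (0.3; 1.3) | 1.7% / 2.4% | 2.45% / 2.34% | 2.52% / 2.43% | 86.2% v 85.8% | 84.7% v 84.0% |
| Modest (0.5; 1.5) | 4.5% / 6.0% | 2.40% / 2.30% | 2.49% / 2.54% | 85.3% v 85.7% | 84.4% v 85.2% |
| Strong (1.0; 2) | 14.3% / 17.5% | 1.80% / 1.71% | 2.38% / 2.36% | 86.2% v 87.8% | 85.2% v 89.3% |
| Very strong (1.5; 3) | 26.0% / 30.2% | 1.68% / 1.31% | 2.74% / 2.76% | 86.6% v 91.0% | 86.9% v 92.8% |

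The gain from adjusting is −1.2 / −0.6 points with no association, −0.4 / −0.7 weak, +0.4 / +0.8 modest, +1.6 / +4.1 strong and +4.4 / +5.9 very strong. At the top end the simulated level lies above the formula, as expected when balance is incomplete.

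**Step 4: sensitivity to the assumptions.** A second set of runs used 450 patients, change rates of about 27-30% v 39-40%, and a concurrent-start effect of −0.7 to −1 in log-odds (odds ratio 0.50 to 0.37). At centre SD 0.5, 0.8 and 1.0 the Z-test level was 2.2%, 2.1% and 1.8%, and power was 72% v 74%, 67% v 72% and 61% v 67%. With no centre variation it was 77% v 76%. The 2-point gap at SD 0.5 comes with a strong concurrent-start effect, so it is not a modest-association case. A third set gave a Z-test level of 2.5-3.0% and a power change of about −1 to +1 point at no or modest association, so no shortfall was visible there. With centre SD 1.0 and odds ratios of 2 it gave 1.7% and a 6.6-point loss.

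The simulated alternative has the higher rate on placebo, which is H0,4a. The formula applies equally to H0,4b, but no tapering rates were simulated.

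**The case against.** Four arguments can be made for leaving the Z-tests alone.

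- **The unadjusted test is valid.** An error towards conservatism makes a verdict upgrade harder to reach. This stands. With both tests in use, the chance of a false finding of confounding is at most 2.5% + 2.5% = 5%, and conservatism only lowers it. A reader might infer that the omission inflates false success; the direction is the opposite.
- **The effect may be negligible.** A reader might also infer that the tests do run below 2.5% and do lose power. The documents do not support that as fact: they give no change rates, no strength of association and no minimisation probability. Qualifying changes before V2 are not counted, so a baseline start is not itself part of the outcome. With no or weak association the crude test is very slightly the more powerful. This stands too, and it is why the point is conditional.
- **The SAP 4.10 commitment may cover only hypotheses 1 to 3.** The sentence closes a paragraph on those hypotheses, and the next paragraph defers treatment changes to 4.11. That reading is reasonable. But the sentence says all analyses, and the same section makes the confounding assessment step 3 of one strategy, so the scope is at least unclear.
- **Adjustment is awkward with very small centres.** This counts against a comparison stratified by centre. It counts less against a random intercept, which SAP 4.10.1.1 adopts for that very reason.

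**Conclusion.** The point holds in conditional form and is minor. The two Z-tests omit the factors on which patients were allocated, while the SAP's general statement and its models 1 to 3 include them. If the factors predict co-medication change between V2 and V6, the tests are conservative.

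Up to modest association the level is about 2.3-2.5% and the power loss about 1 point or less, within or close to simulation error. A material effect, with a level of about 1.7-1.8% and about 2 to 7 points of power lost, needs a centre SD of about 1 on the log-odds scale. That is possible across 28 centres in seven countries but remains an assumption. All these figures also rest on the assumed change rates and on an assignment probability of 0.8.

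The consequence is a somewhat lower chance of detecting a true differential co-intervention, and hence of reaching the upgraded benefit verdict.

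**What to change.** In SAP 4.11.1, test H0,4a and H0,4b each with the same prespecified binomial mixed model, built like model 3: treatment, prior glucocorticoid exposure and concurrent start as fixed effects, and a random intercept for centre. Keep each test one-sided at 2.5%, and keep the crude proportions per arm as description. Name the link function, because SAP 4.10 speaks of an odds ratio for harm while 4.10.3 uses a log link. A comparison stratified by centre alone would not be enough, since it leaves out two of the three factors.

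If the Z-tests are kept, limit the SAP 4.10 sentence to hypotheses 1 to 3 and give the reason.

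The cost is a change of wording and slightly more analysis work on variables already used in models 1 to 3, plus up to about 1 point of power if the factors turn out not to be prognostic. The simulations used a linear model with fixed centre effects, whose level reached about 2.8% in the most extreme setting. The mixed model itself was not simulated, so its level should be checked before it is adopted.
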